**Date**

**Refer to the Study Reference Manual for Medical Monitor's name and contact information.**

# PROTOCOL AMENDMENT SUMMARY OF CHANGES TABLE

**Table 1 Document History**

Document	Date	Substantial	Region
Amendment 3.0	18-May-2022	Yes	Global
Amendment 2.0	15-Nov-2021	Yes	Global
Amendment 1.0	08-Oct-2021	Yes	Global
Original Protocol (Final Version 2)	12-Jul-2021	-	-

## **Amendment 3.0 (18-May-2022)**

This amendment is considered substantial based on the criteria set forth in Article 10(a) of Directive 2001/20/EC of the European Parliament and the Council of the European Union.

### **Overall Rationale for the Amendment:**

The protocol was amended primarily to reflect the expansion of the study to the countries other than the United States of America (US). Outside of the US, participants will have the same vaccination schedule but will be co-administered *Prevnar 13* only if the pneumococcal conjugate vaccine is recommended at 12-15 months as per national immunization schedule. Also, the storage conditions for *Varivax* were updated with the country-specific details, and corrections were made to the temperature excursions for study vaccines. Additionally, this amendment conditionally allowed administration of a second dose of *Varivax* and/or *Havrix* in non-US countries (not part of the study procedures).

**Table 2 Description of the Most Important Changes in Amendment 3.0**

Section # and Name	Description of Change	Brief Rationale
1.1. Synopsis 1.3. Schedule of Activities 2.1. Study Rationale 5.1. Inclusion Criteria	
Updated the text to reflect the following (in bold; in the exact or similar wording):
 
In this study, all participants recruited in the US will be co-administered with a measles, mumps and rubella vaccine (M-M-R II, also called M-M-RVaxPro in countries outside the US, and hereafter designated as MMR), a hepatitis A vaccine (Havrix) and a 13-valent pneumococcal conjugate vaccine (Prevnar 13).
 
Participants recruited outside of the US will be co-administered with MMR, Havrix, and in some countries, with Prevnar 13.
 
Outside the US, Prevnar 13 will only be administered in countries where pneumococcal conjugate vaccine is recommended at 12-15 months as per national immunization schedule.
	
To reflect addition of non-US sites to the study and clarify the inclusion criteria applicable to the participants at non-US sites.
 
To note that in some countries, there can be a different name for the MMR vaccine.

1.2. Synopsis 1.3. Schedule of	At the end of the study or shortly after the study, depending on the vaccines' availability, GSK will provide a second dose of	To allow administration of the

Section # and Name	Description of Change	Brief Rationale
Activities 2.1. Study Rationale	Varivax and/or Havrix to participants enrolled in non-US countries if local health departments do not routinely provide varicella and/or hepatitis A vaccine. Study participants who do not achieve the pre-specified seroresponse threshold criteria will be re-vaccinated with a dose of Varivax.	second dose of the varicella or hepatitis A vaccine (not part of study procedures).
6.2. Preparation/Handling/Storage/Accountability	
Added the text (in bold):
 
Varivax will be stored at -15°C to -30°C (+5°F to -22°F) in the US and other countries with frozen formulation and at +2°C to +8°C (+36°F to +46°F) in the rest of the world. (Note: refrigerated Varivax vaccine will be used at non-US sites, while frozen Varivax vaccine will be used at sites in the US and other countries with frozen formulation.)
	To specify the storage conditions for the study vaccine at the US and non-US sites.
Throughout the protocol where applicable	Removed the statements implying the study will be conducted in the US only; made updates regarding other countries to the scientific rationale for study design; mentioned Independent Ethics Committee(s) as entities overseeing the ethics conduct of the study besides Institutional Review Boards; mentioned the non-US-specific regulatory requirements the study will be performed in accordance with.	To reflect addition of non-US sites to the study and note applicable administrative changes to the conduct of the study.

The detailed description of changes (i.e., added/removed text) and minor updates is provided in [Appendix 5](#).

## 1.0 PROTOCOL SUMMARY

### 1.1 Synopsis

**Protocol Title:** A phase II, observer-blind, randomized, controlled study to evaluate the immunogenicity and safety of a varicella vaccine at various potencies compared with *Varivax*, as a first dose, administered in healthy children in their second year of life.

**Short Title:** A study on the immune response and safety of various potencies of an investigational chickenpox vaccine compared with a marketed chickenpox vaccine, given to healthy children 12 to 15 months of age.

**Rationale:** Varicella (chickenpox) is an acute, highly contagious infectious disease caused by the varicella zoster virus. Safe and effective varicella vaccines have shown to have significant global and national public health impact when implanted in national immunization plans, e.g., as in the United States of America (US). GlaxoSmithKline Biologicals SA (GSK) is developing a candidate varicella vaccine (VNS vaccine). The main purpose of this study is to demonstrate the immunogenicity of the investigational VNS vaccine in 3 potencies compared with commercially available Merck's varicella vaccine, *Varivax* (hereafter designated as VV vaccine), when given as a first dose to children 12 to 15 months of age. In this study, all participants recruited in the US will be co-administered with a measles, mumps and rubella vaccine (M-M-R II, also called *M-M-RVaxPro* in countries outside the US, and hereafter designated as MMR), a hepatitis A vaccine (*Havrix*) and a 13-valent pneumococcal conjugate vaccine (*Prevnar 13*). Participants recruited outside of the US will be co-administered with MMR, *Havrix*, and in some countries, with *Prevnar 13*. Outside the US, *Prevnar 13* will only be administered in countries where pneumococcal conjugate vaccine is recommended at 12-15 months as per national immunization schedule. At the end of the study or shortly after the study, depending on the vaccines' availability, GSK will provide a second dose of *Varivax* and/or *Havrix* to participants enrolled in non-US countries if local health departments do not routinely provide varicella and/or hepatitis A vaccine. Study participants who do not achieve the pre-specified seroresponse threshold criteria will be re-vaccinated with a dose of *Varivax*.

**Objectives, Endpoints, and Estimands:** The study will evaluate the immune response of the investigational VNS vaccine (formulated at 3 different potencies) and the VV vaccine in terms of geometric mean concentration (GMC) and in terms of seroresponse rate (percentage of participants for whom the post-dose anti-glycoprotein E [gE] antibody concentration is  $\geq 300$  mIU/mL) to gE. The study will also evaluate the safety and the reactogenicity (incidence of solicited adverse events [AEs], unsolicited AEs, and serious adverse events [SAEs]) following the administration of the VNS and VV vaccines.

**Overall Design:** This will be a phase II, observer-blind, randomized, multicenter controlled study with 5 parallel intervention groups of healthy children aged 12 to 15 months at the time of intervention. Participants will be randomized to receive a single dose of an investigational varicella vaccine (3 groups each receiving one of the 3 different vaccine potencies [a low, medium, and high potency of the VNS vaccine, respectively]) or a single dose of a comparator licensed varicella vaccine (2 groups each receiving one of the 2 different lots of the VV vaccine, which will be pooled for all analyses). All participants in the US will be co-administered with MMR, *Havrix*, and *Prevnar 13* vaccines. Participants recruited outside of the US will be co-administered with MMR, *Havrix*, and in some countries, with *Prevnar 13*. Outside the US,

*Prevnar 13* will only be administered in countries where pneumococcal conjugate vaccine is recommended at 12-15 months as per national immunization schedule. If *Prevnar 13* is to be administered, participants are required to have previously received the primary series of pneumococcal conjugate vaccine in their first year of life with last dose at least 60 days prior to study entry.

Randomization to one of the 5 groups will be performed in a 2:2:2:1:1 ratio prior to intervention. There will be 3 study visits, at Day 1 (intervention), Day 15 (virtual or in-person), and Day 43, as well as 1 safety call and 1 safety follow-up contact, at Day 2-3 and Day 181, respectively.

**Number of Participants:** Approximately 800 participants will be randomly assigned to the 5 study groups to provide approximately 200 enrolled participants per each VNS group and 100 enrolled participants per each VV group. Approximately 90% of the enrolled participants are expected to be included in the Per Protocol Set (PPS) and evaluated for immunogenicity.

### **Intervention Groups and Duration:**

**VNS\_Low:** VNS low potency vaccine, MMR\*, *Havrix*, and *Prevnar 13*\*\*

**VNS\_Med:** VNS medium potency vaccine, MMR\*, *Havrix*, and *Prevnar 13*\*\*

**VNS\_High:** VNS high potency vaccine, MMR\*, *Havrix*, and *Prevnar 13*\*\*

**VV\_Lot1:** VV vaccine Lot 1, MMR\*, *Havrix*, and *Prevnar 13*\*\*

**VV\_Lot2:** VV vaccine Lot 2, MMR\*, *Havrix*, and *Prevnar 13*\*\*

\**M-M-R II* or *M-M-RVaxPro*, depending on the country.

\*\**Prevnar 13* will only be administered to participants enrolled in the US and in countries where pneumococcal conjugate vaccine is recommended at 12-15 months as per national immunization schedule.

**Statistical Methods:** Three analyses sets will be used in this study, the Enrolled Set, the Exposed Set (ES), and the PPS. The intercurrent medical conditions that may lead to elimination from the PPS will be confirmed immunodeficiency conditions, or development of varicella or herpes zoster in the interval between study intervention administration and the collection of the blood specimen for immunogenicity at Visit 3. The immunogenicity analyses will be based on the PPS. The statistical analyses in this study will be descriptive. The study includes 2 immunogenicity objectives (one primary and one secondary) and one safety objective. The GMCs will be summarized by group with their 95% confidence interval (CI) derived considering log-transformed anti-gE antibody concentrations are normally distributed with unknown variance. The seroresponse rates to gE will be summarized by group with their 95% CIs. The safety analyses will be based on the ES.

**Data Monitoring Committee:** An Independent Data Monitoring Committee comprising of clinical experts and an independent biostatistician will perform periodic safety reviews of the unblinded study data.

## **1.2 Schema**

See [Figure 1](#) in [Section 4.1](#).

## 1.3 Schedule of Activities

**Table 3 Schedule of Activities**

Age	12-15 months of age at the time of study intervention administration					Notes
Type of contact	Visit 1	Safety call	Visit 2*	Visit 3	Safety follow-up contact	
Time points	Day 1	Day 2-3	Day 15	Day 43	Day 181	
Informed consent	●					See Appendix 2 for details
Check inclusion/exclusion criteria	●					See Section 5.1 and Section 5.2 for details
Collect demographic data	●					See Section 8.2.1.1 for details
Medical history	●					See Section 8.2.1.1 for details
Vaccination history (protocol-specific vaccines including pneumococcal conjugate vaccine **)	●					See Section 8.2.1.1 for details See Section 5.1 for details
Physical examination	●					See Section 8.2.1.1 for details
Randomization	○					See Section 6.3.2 for details
Study interventions						See Appendix 1 for the definition
Check contraindications, warnings and precautions to study intervention administration	○					See Section 8.2.1.2 for details
Check criteria for temporary delay for enrollment and study intervention administration	●					See Section 5.5 for details
Study group and treatment number allocation	○					See Section 6.3.3 for details
Body temperature before study intervention administration	●					The preferred location for measuring temperature will be the axilla. Fever is defined as body temperature $\geq 38.0^{\circ}\text{C}/100.4^{\circ}\text{F}$
Study intervention (VNS vaccine/VV vaccine, MMR, Havrix , and Prevnar 13 **) administration	●					Study participants who do not achieve the pre-specified seroresponse threshold criteria will be re-vaccinated with a dose of Varivax
Recording of administered study treatment number	●					

Age	12-15 months of age at the time of study intervention administration					Notes
Type of contact	Visit 1	Safety call	Visit 2*	Visit 3	Safety follow-up contact	
Time points	Day 1	Day 2-3	Day 15	Day 43	Day 181	
Distribute eDiaries/download the app	○					An eDiary/personal electronic device application (app) will be used to capture solicited administration site or systemic events. The participant's parent(s)/LAR(s) should be trained on the use of the eDiary/app. See Appendix 4 for details
Second dose of Varivax and/or Havrix					x	At the end of the study or shortly after the study, depending on the vaccines' availability, GSK will provide a second dose of Havrix and/or Varivax in countries where they are not routinely provided. The administration of the second dose of Havrix and Varivax is not part of the study procedures, however, the administration of the second dose (or the date of the planned visit for administration) should be recorded in the eCRF.
Laboratory assessment						
Blood sampling for antibody determination (~3 mL)				●		See Section 8.1.1 for details
Safety assessments						
Record any concomitant medications/vaccinations	●	●	●	●		See Section 6.8 for details
Record any intercurrent medical conditions				●		See Section 9.3 for more information
Phone contact for safety follow-up		●			●	Or any other convenient procedure
Recording of solicited administration site events from Day 1-4 post study intervention administration	○	○				Only events following the administered dose of VNS vaccine or VV vaccine will be solicited
Safety follow-up with clinical staff to review post-vaccination safety data			●			
Recording of solicited systemic events (drowsiness, loss of appetite and irritability) from Day 1-15 post study intervention administration	○	○	○			See Section 8.3 and Appendix 4

Age	12-15 months of age at the time of study intervention administration					Notes
Type of contact	Visit 1	Safety call	Visit 2*	Visit 3	Safety follow-up contact	
Time points	Day 1	Day 2-3	Day 15	Day 43	Day 181	
Recording of solicited systemic events (fever, varicella-like rash [including injection site varicella-like rash] and general rash [not varicella-like]) from Day 1-43 post study intervention administration	○	○	○	○		See Section 8.3 and Appendix 4
Recording of non-serious AEs from Day 1-43 post study intervention administration	●	●	●	●		See Section 8.3 and Appendix 4
eDiary/app completion reminder		●				
Review of eDiaries/app data		○	●	●		
Return of eDiaries/uninstall or disable the app				○		See Section 8.5 for details
Recording of SAEs	●	●	●	●	●	See Section 8.3 for details and Appendix 4 for the definition
Recording of SAEs related to study participation, or to a concurrent GSK medication/vaccine	●	●	●	●	●	The collection and reporting periods start once the participant's parent(s)/LAR(s)'s informed consent is obtained
Study conclusion					●	See Section 4.3 for the definition.

AE = adverse event; App = application; eDiary = Electronic Diary; gE = glycoprotein E; LAR = legally acceptable representative; MMR = *M-M-R II* or *M-M-RVaxPro*; SAE = serious adverse event;

VNS vaccine = investigational vaccine; VV vaccine = comparator vaccine (*Varivax*); MMR, *Havrix*, and *Prevnar 13* = co-administered vaccines.

Notes:

\* Visit 2 (Day 15) may be conducted in-person or virtually.

\*\* *Prevnar 13* will only be administered to participants in the United States and in the countries where pneumococcal conjugate vaccine is recommended at 12-15 months as per national immunization schedule.

● is used to indicate a study procedure that requires documentation in the individual electronic case report form (eCRF).

○ is used to indicate a study procedure that does not require documentation in the individual eCRF.

\* is used to indicate a procedure (that is not part of the study) that requires documentation in the individual eCRF

Refer to [Table 4](#) for allowed intervals between study visits.

Refer to the Study Reference Manual /pharmacy manual for the volume of the vaccine after reconstitution.

**Table 4** Intervals Between Study Visits

Interval	Planned visit interval*	Allowed interval range
Visit 1→ Safety call	1 to 2 days	1 to 3 days
Visit 1→Visit 2	14 days	14 to 19 days
Visit 1→Visit 3	42 days	35 to 56 days
Visit 1→ Safety follow-up contact	180 days	180 to 201 days

\*Number of days between the visits.

Note: Whenever possible, the investigator should arrange study visits following the planned visit interval. Deviation from allowed interval between Visit 1 and Visit 3 will lead to elimination from the Per Protocol Set.

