### 3.0 OBJECTIVES AND ENDPOINTS

**Table 5** Study Objectives and Endpoints

Objectives	Endpoints
Primary	

 
To evaluate the immune response of VNS vaccine (formulated with different potencies) and VV vaccine in terms of geometric mean concentration at Day 43
 
	
 
Anti-gE antibody concentration at Day 43
 

Secondary	

 
To evaluate the immune response of VNS vaccine (formulated with different potencies) and VV vaccine in terms of seroresponse rate* at Day 43
 
To evaluate safety and reactogenicity following administration of VNS and VV vaccines
 
	
 
Seroresponse to gE at Day 43
 
 
Solicited events
 
 
Percentage of participants reporting each solicited administration site event in terms of injection site redness, pain and swelling within 4 days (Day 1 to Day 4) post-dose of VNS vaccine or VV vaccine
 
Percentage of participants reporting each solicited systemic event in terms of fever, varicella-like rash†, and general rash (not varicella-like) within 43 days (Day 1 to Day 43) post-dose of study interventions**
 
Percentage of participants reporting each solicited systemic event in terms of drowsiness, loss of appetite, and irritability within 15 days (Day 1 to Day 15) post-dose of study interventions**
 
 
Unsolicited adverse events (AEs)***
 
 
Percentage of participants reporting unsolicited AEs within 43 days (Day 1 to Day 43) post-dose of study interventions**
 
 
Serious adverse events (SAEs)
 
 
Percentage of participants reporting SAEs post-dose of study interventions** up to the end of study
 

AE = adverse event; gE = glycoprotein E; SAE = serious adverse event; VNS vaccine = investigational vaccine, VV vaccine = comparator vaccine (*Varivax*).

\*Seroresponse rate is defined as the percentage of participants for whom post-dose of the study interventions (Day 43), the anti-gE antibody concentration is  $\geq 300$  mIU/mL.

\*\*Study interventions = VNS vaccine (investigational vaccine); VV vaccine (*Varivax*, comparator vaccine); MMR (*M-M-R II* or *M-M-RVaxPro*), *Havrix* and *Prevnar 13* (if applicable) vaccines (co-administered vaccines).

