## 8.3 Adverse Events

### 8.3.1 Time Period and Frequency for Collecting AE and SAEs and Other Safety Information

The definitions of an AE or SAE are provided in [Appendix 4](#).

Collection of AEs starts on the day of the study intervention (Day 1) up to Day 43 unless the AE leads to study discontinuation. Collection of SAEs starts the day of the study intervention (Day 1) and up to Day 181 unless the SAE leads to study discontinuation. The frequency for collection of AEs and SAEs is shown in the SoA ([Section 1.3](#)).

Provided that GSK marketed study interventions registered in the US are combination products (see [Table 7](#), and the definition of a combination product in [Appendix 1](#)), associated AEs meeting pre-specified definitions will be classified as medical device AEs and SAEs, as well as adverse device effects (ADEs), serious adverse device effects (SADEs), and unanticipated serious adverse device effects (USADEs). Definitions of these events are provided in [Appendix 4](#). Details on recording, follow-up and reporting of medical device deficiencies are provided in [Section 8.3.6](#).

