### **8.5 Study Procedures During Special Circumstances**

During special circumstances (e.g., COVID-19 pandemic), the specific guidance from local public health and other competent authorities regarding the protection of individuals' welfare must be followed. For the duration of such special circumstances, the following measures may be implemented for enrolled participants:

- Safety follow-up may be made by a phone call or other means of virtual contact.
- If the eDiary device was provided to the participant's parent(s)/LAR(s), it may be returned to the study center by conventional mail after the end of the relevant data collection period (refer to the SRM for details). If the app was provided to the participants' parent(s)/LAR(s) for use on their personal device, the app can be disabled remotely.
- Visits for suspected AEs may take place in a different location\* other than the study center or at participant's home. If this is not feasible, then the medical evaluation of AEs may take place remotely with documentation of symptoms by other means of communication (e.g., phone call or videoconference), if possible.
- Biological samples may be collected at a different location\* other than the study center or at participant's home. Biological samples should not be collected if they cannot be processed in a timely manner or appropriately stored until the intended use.

\*Note: It is the investigator's responsibility to identify an alternate location. The investigator should ensure that this alternate location meets ICH GCP requirements, such as adequate facilities to perform study procedures, appropriate training of the staff, and documented delegation of responsibilities in this location. This alternate location may need to be covered by proper insurance for the conduct of study on participants by investigator and study center staff other than the designated study center.

The impact on the PPS for immunogenicity will be determined on a case-by-case basis. Any impact of the above-mentioned measures on the study results will be described in the Clinical Study Report (CSR).

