7.1. REFERENCE START DATE AND STUDY DAY

Study Day will be calculated from the reference start date and will be used to show start/stop day of assessments and events.

Reference start date is defined as the day of the dose of study vaccination at day 1 and will appear in every listing where an assessment date or event date appears.

If the date of the event is on or after the date of vaccination at Day 1 then:

Study Day = (date of event – date of vaccination at Day 1) + 1.

If the date of the event is prior to the date of vaccination at Day 1 then:

Study Day = (date of event – date of vaccination at Day 1).

In the situation where the event date is partial or missing, Study Day, and any corresponding durations will appear partial or missing in the listings.

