7.4. WINDOWING CONVENTIONS

Allowed time window for each visit will be performed as mentioned in “Schedule of Activities”, section 1.3 of protocol.

Intervals between Study Visits

Interval	Planned visit interval	Allowed interval range
Visit 1 → Safety call	1 to 2 days	1 to 3 days
Visit 1 → Visit 2	14 days	14 to 19 days
Visit 1 → Visit 3	42 days	35 to 56 days
Visit 1 → Safety follow-up contact	180 days	180 to 201 days

Document: \\quintiles.net\enterprise\Apps\sasdata\SASb\SAS\GlaxoSmithKline\VNS\217212\VNS 20-006\Biostatistics\Documentation\SAP\ GSK_217212\VNS 20-006_ZZA47662_SAP_Final_v7_24Jun2024.docx

Author: PPD Version Number: 7.0
Version Date: 24Jun2024

Template No.: CS_TP_BS016 Revision 6 Reference: CS_WI_BS005

Effective Date: 02Dec2019

Window convention

Assigned Study Day	Visit label as per protocol	Visit assigned
Day 1	Visit 1	Visit 1 (Day 1)
Day 2 to 3 (Day 1 + 1 to 3 days)	Safety Call	Safety Call (Day 2 – 3)
Day 15 (Day 1 + 14 to 19 days)	Visit 2	Visit 2 (Day 15)
Day 43 (Day 1 + 35 to 56 days)	Visit 3	Visit 3 (Day 43)
Day 181 (Day 1 + 180 to 201 days)	Safety Follow-up contact	Safety Follow-up (Day 181)

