 Version Date: 24Jun2024

Template No.: CS_TP_BS016 Revision 6

Reference: CS_WI_BS005

Effective Date: 02Dec2019

Unsolicited adverse events that are synonymous with solicited adverse events

Solicited Adverse Event	MedDRA PT/HLT
Pain at injection site	Administration site pain (PT)
Redness at injection site	Administration site erythema (PT)
Swelling at injection site	Administration site swelling (PT)
Drowsiness	Somnolence (PT)
Loss of appetite	Decreased appetite (PT)
Fever	Pyrexia (PT)
Irritability	Irritability (PT)
Rash (all types combined)	Rashes, eruptions and exanthems NEC (HLT)

18.1.1.1. eCOA Compliance

Overall electronic diary (eCOA) compliance (across all eCOAs and all participants) for the study is calculated as:

$$\frac{\text{Total number of complete eCOAs}}{(\text{Expected number of complete eCOAs per participant} \times \text{Total number of participants})}$$

Where the expected number of complete eCOAs per participant is defined as 43, the number of days in which the eCOA is expected to be completed. This definition will also apply to participants who discontinue the study early.

An eCOA is considered complete if there is no missing data within the assessment. Solicited

Document: \\quintiles.net\enterprise\Apps\sasdata\SASb\SAS\GlaxoSmithKline\VNS\217212\VNS 20-006\Biostatistics\Documentation\SAP\ GSK_217212\VNS 20-006)_ZZA47662_SAP_Final_v7_24Jun2024.docx

Author: PPD Version Number: 7.0
 Version Date: 24Jun2024

Template No.: CS_TP_BS016 Revision 6

Reference: CS_WI_BS005

Effective Date: 02Dec2019

event data reported by the investigator will not contribute to eCOA compliance.

A participant is considered to be compliant with their eCOA if at least 80% of their eCOA are complete, i.e, a participant is compliant if they meet the following criteria:

$$\frac{\text{Total number of complete eCOAs}}{\text{Expected number of complete eCOAs}} \times 100 \geq 80\%$$

The overall compliance, and the number of participants who are 0 - <50% compliant, 50 - <80% compliant and $\geq 80\%$ compliant with eCOA assessments will be summarized for the Final Analysis.

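### Diaries are scheduled for return at Visit 3, allowed from Day 36, while the fever, rash and non-serious AE endpoints run to Day 43, so up to 7 days may go unrecorded for children seen early

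*Protocol*

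**What the plan says.** **Schedule.** Protocol Table 3 marks the row "Return of eDiaries/uninstall or disable the app" under Visit 3 only. Visit 3 is also the last column marked for the Day 1–43 solicited systemic events and for non-serious AEs. The only later scheduled contact is Day 181, where serious adverse events (SAEs) are marked but non-serious AEs are not.

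**Window.** Protocol Table 4 plans Visit 3 at 42 days and allows 35 to 56. SAP 7.4 uses the same range, "Day 43 (Day 1 + 35 to 56 days".

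**Endpoints.** In Protocol Table 5, fever, varicella-like rash and general rash are counted "within 43 days (Day 1 to Day 43) post-dose of study interventions". The unsolicited endpoint is "Percentage of participants reporting unsolicited AEs within 43 days (Day 1 to Day 43) post-dose of study interventions". Section 8.3.1 has the same end point: "Collection of AEs starts on the day of the study intervention (Day 1) up to Day 43". Appendix 4 and SAP 18 agree.

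**Analysis.** SAP 18.1.1 bases solicited incidence on vaccinated participants. Daily prevalence uses only those who documented the event as present or absent on that day. For diary compliance, SAP 18.1.1.1 fixes the denominator: "Where the expected number of complete eCOAs per participant is defined as 43". A participant with at least 80% of entries complete is compliant.

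**The concern.** The schedule ends collection at a visit, and the endpoints end it on a day. The two coincide only if Visit 3 falls on Day 43 or later. The other later contacts do not have this problem. Visit 2 is allowed from 14 days (Day 15), so it cannot precede the end of the 15-day solicited period, and the final contact is allowed from 180 days (Day 181). Only Visit 3 can come before the end of the period that it closes.

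A child who hands back the diary early with no event so far still counts in the incidence denominator but can no longer contribute a fever or rash. That pushes the 43-day incidence down. The vaccine has not been given to humans before, and the first Independent Data Monitoring Committee review opens once the first 200 children have attended Visit 3 within its window or have withdrawn. That review could therefore include some shortened follow-up.

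**Working it through.** **Day numbering.** SAP 7.1 gives "Study Day = (date of event – date of vaccination at Day 1) + 1". Intervals of 14, 42 and 180 days give Days 15, 43 and 181, which reproduces the plan's visit labels.

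**Length of the gap.**
- Earliest Visit 3: 35 + 1 = Day 36. Latest: 56 + 1 = Day 57.
- Days 37 to 43 are 7 days; 7/43 = 16.3% of the window.
- Appendix 4 asks for temperature in the evening. If the diary is returned at a daytime visit on Day 36, that evening's reading is lost too, making 8 evening readings.

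**Diary compliance.**
- Return on Day 36: 36/43 = 83.7%, or 35/43 = 81.4% without that day's entry.
- The 80% threshold is 0.80 × 43 = 34.4, so 35 entries suffice. An otherwise fully compliant child cut off on Day 36 stays in the top category, and the compliance categories would not flag the loss.

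**Effect on fever incidence.** Protocol 2.3.1 cites fever in 15% of children within 42 days of varicella vaccination. I take 15% as the true rate over the 43-day window. The distribution of Visit 3 dates is not given, so I show a range.

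1. *Visit dates uniform over the window, fever spread evenly (both assumptions).* Of the 22 possible intervals (35 to 56), 7 put Visit 3 before Day 43: 7/22 = 31.8%. Their losses are 7, 6, …, 1 days, which sum to 28, a mean of 4. Over all children the mean loss is 28/22 = 1.27 days, and 1.27/43 = 3.0%. Shortfall: 15% × 3.0% ≈ 0.44 points, or 0.0044 × 200 ≈ 0.9 child per group of 200.
2. *Every Visit 3 on Day 36, constant daily hazard (upper bound).* Observed proportion = 1 − (1 − 0.15)^(36/43) = 12.7%. Shortfall: 2.3 points, or about 4.6 of 200.
3. *A share of visits on Day 36, the rest on Day 43 or later, same hazard.* With 25% of visits that early the shortfall is 0.6 points; with 50% it is 1.1.
4. *Other true rates, every visit on Day 36.* The shortfall runs from 0.8 points at a true rate of 5% to 4.2 points at 30%.

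For rash an even spread overstates the loss. Protocol 2.3.1 says injection-site lesions generally occur within 2 weeks and most generalized rashes within 3 weeks.

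**The case against.** The strongest reply is that the governing text says Day 43. Section 8.3.1 and Appendix 4 require collection to that day, and Table 3 is a nominal-day schedule whose Visit 3 column is Day 43. The diary-return row also points to Section 8.5, which lets the device be mailed back once the collection period is over and says "the app can be disabled remotely". SAP 18.1.1 notes that diaries started late stayed open beyond the solicited period. Operational detail sits in the Study Reference Manual, which is not available here.

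This reply shows that the days *may*, rather than *must*, be lost. It does not close the gap. Section 8.5 is written for special circumstances, and the SAP remark concerns late starts. Neither tells a site to keep the diary running after an early Visit 3, and a site that follows Table 3 literally would close it.

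A reader might also infer four stronger points that the documents do not support:

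- *That unsolicited AEs are lost with the diary.* They are not diary items. Under Appendix 4, parents contact the site about medically attended or worrying events, and SAEs are collected to Day 181. What is missing is a scheduled contact that asks about the remaining minor events.
- *That unrecorded days are counted as event-free throughout.* No passage says so. It is a fair description of the effect on the incidence proportions, but daily prevalence uses documented days only, and its denominators would shrink over Days 37–43.
- *That early attenders would be classed as non-compliant.* They would not, as the working shows; only the overall compliance percentage falls a little.
- *That the comparison of groups is biased.* The visit window is the same in every group, collection is observer-blind and the analyses are descriptive.

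**Conclusion.** The point holds as a modest mismatch between the schedule and the endpoints. Followed as written, the schedule can cut up to 7 of 43 days of solicited fever and rash for a child seen early. It also leaves minor unsolicited AEs in those days without a contact that asks about them.

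The likely effect is slight understatement of 43-day incidence in all groups: about 0.4 points for fever under uniform visit dates, with an upper bound of 2.3 points. Both figures assume a 15% rate and risk spread evenly over the window. The instruction to keep to the planned 42-day interval where possible makes the upper bound unlikely. For scale, the protocol's own exact 95% interval at 20 of 200 runs from 6.22% to 15.02%, so sampling error is larger than this shortfall. The change is worth making because it is cheap and this is first-in-human safety data.

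**What to change.** **If collection is still running.** Change the Table 3 row so that the diary or app stays active through Day 43 whatever the date of Visit 3, with mail return or remote disabling afterwards by the mechanism already in Section 8.5. State in Table 3 and Section 8.3.1 that non-serious AE collection continues to Day 43 after an early visit. A short remote check on or after Day 43, for early attenders only, would do this. Asking at Day 181 instead would rely on recall of minor events more than four months old.

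**If collection is complete.** Have the SAP report, by group, how many children were observed to Day 43 (from Visit 3 dates and diary entries), and add a sensitivity summary of the 43-day incidence in those children. That summary assumes visit timing is unrelated to events, which should be stated.

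**Cost.** Some devices come back later, and early attenders get one brief remote check. The blood-sampling window and the immunogenicity analysis do not change. The SAP additions are one count and one repeated table.
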